Only one wound per subject will be included in the study. Subjects with multiple wounds will have each wound measured for volume. The wound with the largest volume meeting all eligibility requirements will be chosen for inclusion in the study. The etiology of the chosen wound, and if it is a new or recurring, will be documented.

Randomization and Blinding Procedure

Prior to study initiation, Active and Control samples will be prepared in sealed and labeled as A or B, also randomization envelopes will be provided to the research staff and used to obtain randomization assignment. Within each randomization envelope, there is an assignment of A or B. After run-in evaluation, the subjects wound will be debrided and dressed with SOC. At the end of the procedure, subjects who continue to meet all inclusion and no exclusion criteria will be randomized in a 1:1 ratio to be treated with either Control or Celliant therapies, stratified by wound size (greater than size of 4 cm²) and study center. Study staff will use the randomization number labels and sock assignment of socks A or B contained in the envelope. The number will become the subject ID. The research staff will note the randomization number and the treatment assignment letter (A or B) on the CRF. The key, indicating therapy assignments (Active or Control), will only be available to staff not directly involved in the study until after the subject has completed study activities.

Visit Schedule

Study procedures for each phase of study are outlined below. In a later section, details on each study procedure are described, including equipment designation.

Screening

- 1. Explain purpose and nature of the study and obtain signature on the informed consent document.
- 2. Screen the subject against protocol inclusion and exclusion criteria, including all pertinent tests.
 - a. ABI and/toe pressure
 - b. Ulcer History, measurement, and classification
 - c. Urine Pregnancy test (if indicated)

Baseline (may be done as same day as screening procedures)

- 1. Obtain general medical history and demographic information and social history
- 2. Complete a physical examination, body weight, height, and vital signs, including measurement of resting heart rate, respiratory rate, and blood pressure while seated.
- 3. Select the target ulcer
- 4. Obtain complete history pertinent to DFU disease including duration of the target ulcer,

previous and current treatment.

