Internal audits are done periodically to assure regulations, guidelines and protocols are adhered to appropriately. Patient binders are reviewed for proper informed consent process documentation, case report forms are compared to the source documents and reviewed for accuracy and an independent review of the inclusion and exclusion criteria using a checklist. Additionally, the use of an auditing and monitoring tool which includes sections on consent, HIPAA, on study/treatment, off treatment/off study and a general section. Weekly meetings occur to go over each study. If there are any issues that arise, they are brought up and discussed at the meeting.

4. Statistical Analyses

General Statistical Considerations

This study is a prospective, sham-controlled, subject and evaluator blinded, 1:1 randomized, multicenter clinical study. The duration of the study is up to four months for randomized subjects. Sample size may not be reduced less than the expected total enrollment of 254 evaluable subjects total but may increase up to a total of 2500 evaluable subjects. Sample size will increase based on actual attrition that is expected to be between 5 and 15%.

The purpose of this study is to evaluate safety and efficacy outcomes related to the Celliant Sock (CS). The p-value thresholds for determining statistical significance are 0.05 and 0.025 for 2- and 1-sided tests, respectively, unless otherwise specified.

Protocol #: HGX2020-01

Data will be presented using summary statistics. For example, continuous data may be displayed with the mean, median, minimum, maximum, and/or standard deviation, while categorical data may be displayed as proportions and counts.

Any changes to the analysis of the trial data will be documented either in a future protocol amendment or in the SAP.

Randomization

Randomization will be conducted in a 1:1 ratio of the Treatment Group (Celliant Sock, n=127) or to a sham Control Group (placebo sock, n=127). Randomization will be performed within randomly selected block sizes of 3 and 6 with equal probability of group assignment stratified by study center and wound size (greater than size of 4 cm²).

A Sponsor-designated independent statistical consultant will provide the randomization list. Sponsor personnel directly involved in the management, conduct, and reporting of the study will not have access to randomization assignments until the study is completed.

Analysis Population

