A mixed model repeated measures (MMRM) will be utilized to model percent changes in tissue oxygenation by visit through 12 weeks from baseline to provide the contrast statement at 12 weeks between groups. Included in the model will be treatment group, the stratification variables of wound size (as a continuous variable) and study site. Success on this endpoint requires that the 12-week treatment group contrast difference is α <0.025. There is no interim analysis for the primary endpoint. The primary endpoint is based on a fixed study design. Regulatory activities for all but the key secondary endpoint will begin if this primary endpoint is met.

Interim Analysis for the Key Secondary Endpoint

The key secondary endpoint will only be tested for significance if the success criterion for the primary endpoint are met at the time of the primary endpoint analysis in 254 evaluable subjects, which is the interim analysis for the key secondary endpoint.

The key secondary endpoint is an inferential test of whether the Treatment Group (Celliant sock) incidence of complete wound closure rate (CWCR) compared to the Control Group (placebo sock) at 12 weeks is superior.

The hypotheses for this endpoint are:

```
H0: CWCR Celliant ≤ CWCR Placebo
Ha: CWCR Celliant > CWCR Placebo
```

The key secondary endpoint of incidence of complete wound closure at 12 weeks will be blinded except to the unblinded Interim Analysis Committee (IAC) until the final analysis for this endpoint is conducted. Since the estimated sample size for the key secondary endpoint is anticipated to be many times larger than for the primary endpoint and there is some uncertainty relative to the anticipated treatment effect, the hierarchical design allowing for the testing of the key secondary endpoint, and then the use of the adaptive group sequential design to allow for the potential of sample size re-estimation is required for efficiency.

The IAC is comprised of an unblinded statistician and a subject area medical expert whose sole responsibility is to analyze the key secondary endpoint at 254 evaluable subjects to determine, according to the Lan-Demets O-Brien Fleming alpha spending function, tested at half of the trial information:

- 1) The criterion of early stopping for efficacy for CWCR is met at half of the trial information,

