- 2) The trial will continue to the preplanned 508 planned evaluable subjects for assessing CWCR, based on the conditional power at the interim to be Cp≥ 0.85,
- 3) If neither of the first two criteria are met, then sample size re-estimation according to the inverse normal method (Lehmacher and Wassmer, 1999) will be conducted to allow for a sample size of up to 2500 evaluable subjects total for the study.
 - a. The trial will be stopped for futility of the key secondary endpoint if the Cp assuming a maximum sample size of 1250 subjects for the study provides a CP<0.7.

 - b. The trial will have a sample size increase as calculated by the inverse normal method to maintain a Cp=0.85.

With the exception of meeting criterion 1 or 3a, i.e. stopping further enrollment, the results of the interim analysis will not be shared with the clinical operations team involved directly in the study data at the patient or data management. This communication firewall is required to maintain the validity of the secondary endpoint in that subjects before and after the interim analysis are handled no differently in a way that would alter the estimated treatment effect.

A logistic model will be used to control for the stratification variables and assess for the treatment effect. Once again, as in the primary endpoint, the baseline wound size will be assessed as a continuous endpoint, although the stratification variable is dichotomous.

Type 1 error is controlled because of the hierarchical testing strategy of the primary endpoint and then key secondary endpoints, both at $\alpha_{1-\text{sided}}$ =0.025.

An Interim Analysis Charter (IAC) will be provided solely to provide a communication plan and numerical example with SAS code to detail the calculations involved for the key secondary endpoint.

Hierarchical Testing of the VAS Pain Endpoint

The VAS pain endpoint will be tested as the third hierarchical endpoint, i.e., following testing of the primary endpoint and then the total wound closure endpoint. In order for the VAS pain endpoint to be tested, the primary endpoint and the TWCR endpoints would both need to be statistically significant. The final total sample size as determined by the sample size reestimation for TWCR will be applied to the VAS pain endpoint without further modification.

Evaluability of Data

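### Blocks of 3 cannot be split equally between two arms, so the stated block sizes do not fit the stated 1:1 allocation

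*Combined protocol and SAP*

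**What the plan says.** Section 4, Randomization, opens: "Randomization will be conducted in a 1:1 ratio of the Treatment Group", naming a Celliant sock group and a placebo sock group of 127 each. The next sentence reads: "Randomization will be performed within randomly selected block sizes of 3 and 6 with equal probability of group assignment", with stratification by study center and wound size. On who prepares the list it says: "A Sponsor-designated independent statistical consultant will provide the randomization list".

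Section 3, Randomization and Blinding Procedure, describes the same two-arm scheme from the site's side. Subjects are "randomized in a 1:1 ratio to be treated with either Control or Celliant therapies, stratified by wound size" and study center. On the envelopes: "Within each randomization envelope, there is an assignment of A or B". Only these two letters exist. The Executive Summary, Description of Trial Design and Sample Size Justification also give 1:1.

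Nowhere does the document give a third arm, a different ratio, or the composition of a block of 3.

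**The concern.** Permuted blocks are used so that each completed block restores the target ratio. With two arms at 1:1 this requires an even block size. A block of 6 meets the requirement and a block of 3 does not, so one of the two printed sizes is at odds with the ratio printed in the sentence before it.

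The text is therefore compatible with several lists that balance the arms differently, or the 3 is a typing error and the text does not describe the intended list. In either case a monitor cannot check the list against the protocol. The stake is balance within strata and traceability of the allocation.

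**Working it through.** **Inputs.** Two arms at 1:1, 127 + 127 (Section 4, Randomization). Blocks of 3 and 6 (same place). Two named sites and one wound-size cut at 4 cm² give 2 × 2 = 4 strata. Difference 8.2, SD 21.7, two-sided alpha 0.05, power 0.85, 254 evaluable (Section 4, Sample Size Justification). Assumptions, because the document is silent: the two block sizes are equally likely, the strata are about equal (64/64/63/63), and nobody is lost.

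**The plan's own figure.** The normal formula n = 2(1.960 + 1.036)²(21.7/8.2)² gives 125.8, so 126 per arm. The noncentral t gives power 0.848 at 126 and 0.851 at 127 per arm. The 254 is therefore reproduced and is not in question.

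**Possible splits.** An equal split needs k = b − k, so b must be even. For b = 6 this is 3:3. For b = 3 the only splits are 3:0, 2:1, 1:2 and 0:3, and none is equal.

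**Arm difference at 254, by how a block of 3 is filled.** The mean block size is (3 + 6)/2 = 4.5. That gives 254/4.5 ≈ 56.4 blocks, of which about 28.2 have size 3.

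- *Randomly 2:1 or 1:2.* Each block of 3 adds +1 or −1, so the variance is about 28.2 and the SD about 5.3. Incomplete last blocks raise the simulated SD to about 5.8, and 1.96 × 5.8 = 11.4. The simulated 95th percentile is 12 (the difference must be even at 254), with a mean absolute difference of 4.4.
- *Unconstrained, each subject 50:50.* Each block of 3 adds variance 3, so 3 × 28.2 = 84.6, SD about 9.2, and 1.96 × 9.2 ≈ 18. The simulated 95th percentile is 18.
- *Always 2:1 toward one arm, 6s split 3:3.* The share to that arm is (2 + 3)/(3 + 6) = 5/9, and 254 × 5/9 = 141, leaving 113.
- *Comparison, blocks of 4 and 6.* Only the last, incomplete block in each stratum can be unbalanced, by at most 3. The simulated mean is 1.5 and the 95th percentile 4.

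**Effect on primary power** (noncentrality 8.2/[21.7√(1/n₁ + 1/n₂)], t-test):

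| Split | Noncentrality | Power |
|---|---|---|
| 127/127 | 3.011 | 0.851 |
| 133/121 | 3.008 | 0.850 |
| 141/113 | 2.993 | 0.846 |

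The 133/121 row is the 95th percentile under random 2:1 or 1:2 filling. The 95th percentile under unconstrained filling, 136/118, lies between the last two rows.

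**Predictability** (simulated, one stratum of 64, random 2:1 or 1:2 filling for the 3s). A guesser who knows the scheme names the next letter correctly 65.5% of the time with 3 and 6, and 69.1% with 4 and 6. A guesser who always picks the letter that is behind is right 59.0% and 69.1% of the time.

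**The case against.** The strongest reply is that the protocol sets 1:1 for the randomization as a whole, not for each block, and that the equal-probability clause covers the rest. If a block of 3 is 2:1 or 1:2 by a fair coin, every subject has a one-half chance of either sock. This stands as far as it goes: 1:1 in expectation is attainable. But the clause fits both random 2:1 or 1:2 filling and unconstrained filling, which balance differently, and neither restores balance at the end of a block.

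Second, the quoted contrast of 12 against 4 treats 254 as the number randomized, whereas the protocol means evaluable subjects, with 5 to 15% attrition on top. This also stands. Assuming 282 randomized and 10% random loss, the 95th percentiles become 15 with 3 and 6, and 10 with 4 and 6. The advantage of even blocks is smaller in evaluable data.

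Third, the consultant's list is not in the document and may define the rule. That is so, and the fix allows for it, but the printed sizes still do not fit the printed ratio.

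A reader might infer more: that 1:1 is impossible for the whole trial, that the trial is effectively 2:1, or that the treatment comparison is biased. The document supports none of these. A 2:1 fill in every block would give about 169/85 and power 0.808, but nothing in the text suggests it, and it would contradict the repeated 1:1. Bias does not follow, since assignment is still random. The primary model adjusts for the strata: "Included in the model will be treatment group, the stratification variables of wound size (as a continuous variable) and study site". So does the closure model: "A logistic model will be used to control for the stratification variables and assess for the treatment effect".

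**Conclusion.** The point holds in a narrow form. Two arms at 1:1 cannot be balanced in blocks of 3, and the text does not say how such a block is filled. The imbalance is modest under each filling considered, and power moves only from 0.851 to 0.846 at the worst of them. The splitting argument needs no assumption. The imbalance figures rest on equal strata, equally likely block sizes and no attrition. The sample size of 254 is unaffected. Minor.

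**What to change.** In Section 4, Randomization, replace the block sizes 3 and 6 with sizes that are multiples of 2, for example 4 and 6, used within each site by wound-size stratum. First ask the independent consultant whether a list exists. If one has been issued, correct the text to the sizes actually used, including how any blocks of 3 were filled, and leave existing assignments unchanged.

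The cost is one number in the text and one check of the list, with no extra subjects or visits. The downside is predictability: about 69% correct guesses against 66% for someone who knows the scheme, or against 59% for someone who picks the letter that is behind. Site staff do see the letters ("The research staff will note the randomization number and the treatment assignment letter (A or B) on the CRF"). But Section 3 withholds the key linking letter to sock from staff directly involved until the subject has completed study activities, so a correct guess of the letter does not by itself reveal the treatment.

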The primary population for the effectiveness analyses will be the intent-to-treat (ITT) population, which will include all randomized subjects regardless of whether the socks were ever worn. Subjects will be assessed to the group to which they were randomized, regardless of whether they were provided the wrong socks.

A secondary population for effectiveness analyses will be the (AT) population, including subjects that attempted to put on the sock for any amount of time. These subjects will be analyzed according to the type of socks (Celliant or Placebo) they received. This population is also the safety population, which is the population used for all safety analyses.

A third population is the modified full analysis set (mFAS), which consists of all subjects that report wearing the sock as directed for at least 10 days.

Sample Size Justification

Assuming a 2-sided alpha at 0.05, and a power of 0.85, the true mean difference at 12 weeks between groups in percent change in tissue oxygenation as measured by hyperspectral imaging is estimated to be 8.2 with a standard deviation of 21.7. At a 1:1 allocation of experimental to control subjects, a total of 254 evaluable subjects are required. The sample size will increase to account for attrition at Week 12.

Analyzing the sample size for the key secondary endpoint of incidence of complete wound closure suggests a much large trial is need. Specifically, at 2500 evaluable total subjects, there would be approximately a power of 0.85 to detect a difference in incidence of complete wound closure at 12 weeks if the expected incidence of complete wound closure was 25% in the experimental group, and 20% in the control group, an absolute difference of 5% between the experimental group and the control group.

Primary Efficacy Analyses

The primary efficacy endpoint is an inferential test of whether the Treatment Group (Celliant[®] Diabetic Medical Sock) percent change in tissue oxygenation (via oxygen saturation, S_tO₂) compared to the Control Group (placebo sock) at 12 weeks is superior.

Effectiveness variables will be analyzed relative to the mean of the Weekly visit 0 and -1 tissue oxygenation measurements. For purposes of statistical analysis, this mean will be referred to as the baseline.

The hypotheses are:

```
H0: %ChgPerfCelliant ≤ %ChgPerfPlacebo
Ha: %ChgPerfCelliant > %ChgPerfPlacebo
```

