Prior to the database lock for the final primary endpoint analysis at 254 evaluable subjects, and again at any subsequent lock as dictated by the adaptive design for subjects evaluated after the final primary lock, an evaluability meeting will be held. The goal of the evaluability meeting is to identify the disposition of study subjects with respect to the predefined study populations.

Subject Demographic and Baseline Characteristics

Demographic and baseline characteristics of enrolled subjects will be summarized. The factors will include (but are not limited to): Age, sex, race, BMI (kg/m²), baseline Diabetic and Foot Ulcer Scale-Short Form (DFS-SF). Medical history, PE, and vitals will be provided in a listing.

Additional Efficacy Analyses including Subgroup Analyses

Secondary Endpoints: To compare the incidence of the below between Celliant and Control treated groups:

- 1. For subjects whose wound closes within the 12-week period, wound evaluation at 3 months following complete wound closes for the following parameters
 - a. Incidence of wound dehiscence/reoccurrence
 - b. Size of reoccurrence
- 2. Accelerated wound closure as measured by changes in wound area, depth and volume.
- 3. Assessment of Compliance
- 4. Change in pain assessment as reported using VAS pain scale
- 5. Outcomes of Patient Reported Outcomes
- 6. Study related AE/SAEs

Additional, ad hoc exploratory analyses may also be conducted for efficacy endpoints.

Safety Endpoints and Analyses

An overview of events, to include total numbers of events, and total number of subjects will be tabulated and presented for all AEs, SAEs, procedure-related AEs by treatment type. Device specific risks such as "skin and subcutaneous tissue reaction/allergy" and "mild pain or discomfort" will also be tabulated in a separate summary table.

Additional, ad hoc exploratory analyses may also be conducted for safety endpoints.

Poolability

Pooling of outcome data from different clinical study sites will be performed by evaluating the homogeneity of the primary efficacy endpoint across sites. If the treatment by site interaction is $p \ge 0.2$, then homogeneity will be considered to be demonstrated across sites. If p<0.2, then site level variable will remain in the analysis models.

Handling of Missing Data

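### The primary repeated-measures model of percent change in StO2 leaves out baseline StO2, and the poolability rule makes it unclear whether site always stays in the model

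*Combined protocol and SAP*

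**What the plan says.** All references are to section 4, Statistical Analyses, of the combined protocol and SAP.

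- **Primary Efficacy Analyses, model.** Percent change in StO2 is modelled by visit through week 12 with an MMRM, and the primary result is the week-12 contrast between groups. The terms are given as: "Included in the model will be treatment group, the stratification variables of wound size (as a continuous variable) and study site".
- **Primary Efficacy Analyses, baseline.** "Effectiveness variables will be analyzed relative to the mean of the Weekly visit 0 and -1 tissue oxygenation measurements". That mean is called the baseline. It is used as the reference for percent change and is nowhere named as a covariate.
- **Sample Size Justification.** The calculation uses a two-sided 5% level and 85% power. The group difference in percent change "is estimated to be 8.2 with a standard deviation of 21.7". From these inputs the plan arrives at 254 evaluable subjects, 127 in each arm.
- **Randomization.** Blocks are used "with equal probability of group assignment stratified by study center and wound size".
- **Poolability.** A treatment-by-site p-value of 0.2 or more is taken to show homogeneity. "If p<0.2, then site level variable will remain in the analysis models". The paragraph does not say what happens to the site term at 0.2 or more.

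**The concern.** **Baseline StO2.** Because the outcome is percent change, baseline is in the denominator of every value. Measurement noise and regression to the mean then make percent change correlate negatively with baseline: a subject whose baseline happens to read low tends to show a larger rise. Dividing by baseline does not remove that relationship, and wound size and site do not stand in for it. Both baseline readings are scheduled before the sock is first worn, so adjusting for them needs no new data. What is lost is precision on an endpoint that acts as gatekeeper: wound closure and VAS pain are tested only if the primary succeeds.

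**Site.** The primary model contains site unconditionally, and site stratifies the randomization. The poolability rule makes keeping it depend on a pre-test in the trial data. Two analysts could follow the same document and fit different primary models.

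No error is claimed for the visit and treatment-by-visit terms. They are also missing from the list, but modelling by visit and taking a week-12 contrast imply them.

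**Working it through.** **Step 1. Reproduce the plan's figure.** Inputs from Sample Size Justification: difference 8.2, SD 21.7, 1:1 allocation, two-sided alpha 0.05, power 0.85. The success rule in Primary Efficacy Analyses ("Success on this endpoint requires that the 12-week treatment group contrast difference is α <0.025", with a directional hypothesis) is the upper tail of the same test.

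SE = 21.7 × √(2/127) = 2.72, so the noncentrality is 8.2/2.72 = 3.01. With 252 degrees of freedom the noncentral-t power is 0.851. At 126 per arm it is 0.848, so 127 per arm is the smallest size that reaches 0.85. The 254 therefore reproduces as an unadjusted two-sample calculation.

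**Step 2. Effect of adjusting for baseline.** The documents give no correlation. Assume that the two baseline readings and the week-12 reading W have equal variance (set to 1) and a common correlation r. Let B be the mean of the two baseline readings, and treat percent change as change on a scaled axis. Then:

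- Var(B) = (1 + r)/2
- Var(W − B) = 1 + (1 + r)/2 − 2r = 1.5(1 − r)
- Var(W given B) = 1 − 2r²/(1 + r)
- Variance ratio, adjusted to unadjusted = (1 + 2r) / [1.5(1 + r)]

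Example at r = 0.5: 2/2.25 = 0.889; SD = 21.7 × √0.889 = 20.5; SE = 20.5 × √(2/127) = 2.57.

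| r | Variance ratio | SD | SE at 127/arm | Power at 254 | Total N matching unadjusted power |
|---|---|---|---|---|---|
| unadjusted | 1 | 21.7 | 2.72 | 0.851 | 254 |
| 0.3 | 0.82 | 19.7 | 2.47 | 0.912 | 210 |
| 0.5 | 0.89 | 20.5 | 2.57 | 0.889 | 226 |
| 0.7 | 0.94 | 21.1 | 2.64 | 0.871 | 240 |
| 0.8 | 0.96 | 21.3 | 2.67 | 0.864 | 246 |

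**Step 3. Chance imbalance.** The correlation of change with baseline is −0.42, −0.33, −0.24 and −0.19 for the four values of r. A one-standard-error chance imbalance in baseline StO2 moves the unadjusted contrast by |correlation| × 2.72 = 1.15, 0.91, 0.66 and 0.52 points, against an assumed effect of 8.2. Adjustment removes that shift.

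**Step 4. Does the scaled-change shortcut matter?** Simulating the actual ratio 100 × (W/B − 1), with reading CVs of 15% to 25%, gives power 0.914–0.917, 0.891–0.894, 0.872–0.875 and 0.865–0.866. Those CVs are too small to produce an SD of 21.7 at r = 0.7 and 0.8, where the formula needs about 32% and 40%. Lognormal readings matched to 21.7 give about 0.87 and 0.86 there, so the table stands.

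**Step 5. A different starting assumption.** Suppose instead that the correlation ρ between baseline and week-12 percent change is assumed directly, with adjusted SD = 21.7 × √(1 − ρ²). By normal approximation, power at 254 is 0.853 at ρ = 0, and 0.867, 0.907 and 0.964 at |ρ| = 0.2, 0.4 and 0.6.

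**Step 6. The site rule.** If there is truly no treatment-by-site interaction, p is 0.2 or more with probability 0.80. If the rule means that site is otherwise dropped, the term would go in about four trials out of five, contrary to the listed model. The documents give no between-site variance, so the effect on precision cannot be computed.

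**The case against.** The plan delivers what it promises. It claims power of 0.85 from an SD of 21.7, and that calculation is right. Randomization keeps the unadjusted contrast valid, baseline already enters through the percent change, and nothing breaks if the covariate stays out. All of this is correct and sets the weight of the point: it is an improvement, not a repair.

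The size of the gain is assumed. With no correlation in the documents, 1 to 6 points is illustrative and not a bound. Step 5 spans 0 to about 11 points. A correlation that decays with time would break the common-r formula and would probably raise the gain. Variance already removed by wound size and site could reduce it. The direction does not depend on these choices, unless percent change is unrelated to baseline, in which case the gain is nil.

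On site, the Poolability paragraph never says that the term is removed, and its site-level variable could mean the interaction. With two named sites the main effect costs one degree of freedom, and dropping it would not bias a comparison randomized within center. It is fair that removal is only implied. The interaction reading fits less well, because the listed model has no interaction term that could remain. Either way, one sentence is needed to settle which model is primary.

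**Conclusion.** Both parts hold; the change should be made, but the trial does not fail without it.

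The omission of baseline StO2 costs precision only. For a common correlation of 0.3 to 0.8 between readings, adjustment would lower the standard error of the week-12 contrast from 2.72 to between 2.47 and 2.67 and raise power by about 6 points to 1 point. At the favourable end the chance of missing a true effect falls from about 15% to 9%. Confidence is high that the covariate is missing and that including it is sound. The size of the benefit rests on correlations that the documents do not state.

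The site wording permits two primary models, chosen by a data-dependent test, with removal implied and not stated. No numerical consequence can be attached to it.

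**What to change.** In Primary Efficacy Analyses, write the model in full: percent change in StO2 on treatment, visit, treatment-by-visit, baseline StO2 (mean of visits -1 and 0), baseline StO2-by-visit, baseline wound size and site, with the treatment contrast at week 12 as primary. The visit terms are spelled out for clarity only.

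In Poolability, state that site stays in the models whatever the interaction p-value, and that the treatment-by-site interaction is reported as a description of heterogeneity.

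The cost is wording. Baseline StO2 is already collected, and the planned sample size need not change. The baseline and baseline-by-visit terms use about a dozen degrees of freedom; taking 12 from the calculation in Step 2 lowers power by about 0.0002 or less. The General Statistical Considerations already allow analysis changes to be documented in an amendment or the SAP. This should be done before unblinding, since adding a covariate or choosing a site rule afterwards would look post hoc.
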